#### 6.4.7 Central Corneal Thickness Assessment

### 6.4.8 Best-corrected Visual Acuity (BCVA)

#### 6.4.9 Intraocular Pressure Measurement

Intraocular pressure (IOP) will be measured by Goldmann Applanation Tonometry. At least two measurements will be obtained and recorded (a third measurement will be obtained if there is a  $\geq 3$  mmHg difference between the first two measurements).

#### 6.4.10 Urine Pregnancy Test

WOCBP must be tested prior to the start of study treatment and after the completion of study treatment to confirm a continued non-pregnant state. Commercially available urine dip-stick pregnancy tests are acceptable.

Clinical Study Protocol TTHX-002

Confidential and Proprietary

Amendment 7.0: September 22, 2022

### 6.4.11 Delayed Recovery

Subjects with delayed recovery should undergo additional ocular assessments at Day 28, Day 56, or at unscheduled visits. These assessments may include:

- Additional; methods of BCVA (See Section 6.4.8)
- Central Corneal Thickness (by the primary or alternative method)
- AS-OCT
- Pentacam
- etc.

Additional ocular assessments should be reported as an Unscheduled Visit (See Section 6.5.5)

### **6.4.12** Clinical Laboratory Assessments

Samples for clinical laboratory assessments will be obtained and transmitted to a central laboratory. The laboratory parameters to be tested are summarized below in Table 10.

All clinically significant laboratory results that are outside of the normal ranges are to be reported as AEs. An abnormal lab value should be deemed clinically significant if either of the following conditions is met:

- The abnormality suggests a disease and/or organ toxicity that is new or has worsened from baseline as determined by the Investigator and in consultation with Medical Monitor consult at the Investigator's request
- The abnormality is of a degree that requires additional active management, e.g., change of dose, discontinuation of the drug, close observation, more frequent follow-up assessments, or further diagnostic investigation

Therefore, a clinically significant laboratory value is one that suggests a new disease process, an exacerbation or worsening of an existing condition, or requires further action(s) to be taken.

If a clinically significant laboratory result is found on a laboratory test (e.g., hematology), the Investigator should determine if an underlying condition is the reportable AE instead of the individual laboratory parameters (e.g., anemia instead of decrease in red blood cell count, hematocrit, reticulocyte, and hemoglobin levels).

Clinical Study Protocol TTHX-002

Trefoil Therapeutics, Inc.

Confidential and Proprietary

Amendment 7.0: September 22, 2022

**Table 10: Clinical Laboratory Assessments** 

Hematology		
Hematocrit		
Hemoglobin		
White blood cell (WBC) count with differential		
Platelet count		
Serum Chemistry	Urinalysis	
Albumin	Specific gravity	
Alkaline phosphatase	Ketones	

 
ALT (alanine amino transferase)/ SGPT
 
	• pH	

 
AST (aspartate amino transferase)/ SGOT
 
	Protein	
Bicarbonate/CO2	Glucose	
Bilirubin	Blood	
Blood urea nitrogen	Urobilinogen	
Calcium	Bilirubin	
Chloride	Leukocyte esterase	
Creatinine	
 
Microscopic examination (as applicable)
 
	
• HbA1-c		

 
LDH (Lactate dehydrogenase)
 
		
Potassium		
Sodium		
Total protein		
Uric acid		

Following the assessment of systemic exposure (pharmacokinetics) and review of clinical laboratory results in Study TTHX-001, Trefoil may discontinue collection of clinical laboratory samples.

#### Plasma for PK and ADA 6.4.13

Blood samples will be collected for pharmacokinetic (PK) and anti-drug antibody (ADA) analysis at selected sites. Samples will be centrifuged and/or prepared per instructions from the analytic laboratory. Pre-injection samples should be collected within the 24 hours prior to study treatment administration when possible. PK samples should be collected within ±5 minutes of the nominal timepoint or as soon as practicable.

Following the assessment of systemic exposure (pharmacokinetics) at the 50ng dose level, Trefoil may discontinue collection of PK samples at dose levels ≤ 50ng. Pre- and post-exposure ADA samples will continue to be collected regardless of observed PK exposure. A plasma sample will be obtained at the end of the study for ADA analysis

See Study TTHX-002 Laboratory Manual for blood processing instructions.

Amendment 7.0: September 22, 2022

### 6.4.16 Visual Function and Corneal Health Status (V-FUCHS)

The V-FUCHS is a 15-item questionnaire designed to measure patient-reported visual disability in Fuchs endothelial corneal dystrophy (FECD). Upon completion of the questionnaire, the study coordinator will check the questionnaire for completeness. Any omissions or ambiguous answers will be clarified by the subject prior to leaving the clinic. The V-FUCHS should be self-administered, however, trained investigational site staff will administer the questionnaire to subjects who are unable to self-administer the questionnaire. Collection of V-FUCHS should precede any examination requiring contact with the eye, including measurement of IOP, and should be performed prior to instillation of any of any dye or drops to dilate or anesthetize the eye (if applicable).

# 6.5 Study Visits

All study visits/ assessments will be conducted by qualified investigational site staff. Study visits/ assessments are to be conducted within the protocol-specified window for each visit/ assessment. If an assessment/ visit is not able to be collected/ conducted within the protocol-specified window, it should be collected/ performed as soon as practicable, and the actual date/ time recorded. Comparative assessments should be collected at the same time at each timepoint, when possible (unless otherwise directed). If an onsite visit is not possible, as many assessments as feasible can be conducted remotely.

Amendment 7.0: September 22, 2022

### 6.5.1 Screening Period/Baseline Assessments

Screening / baseline assessments may be performed anytime during the Screening Period, unless approved by the Medical Monitor, except for Informed Consent (which must be obtained prior to any protocol-specific assessments).

### 6.5.2 On-study Visits

The frequency of on-study visits will vary depending on the treatment group to which the study subject belongs.

All study drug administration dates must be at least 5 days after the prior study drug administration day (if applicable). All other visits will be scheduled based on the number of days since Day 0. If a study drug administration cannot be administered within the protocol window, it should be administered as soon as practicable.

Worksheets will be provided describing which assessments are required at each visit for each treatment group.

### 6.5.3 Long-term Follow-up

Following the Day 56 evaluations, all subjects will continue to be followed for long-term efficacy, durability of responses, and SAE/SAR resolution. Follow-up visits will occur approximately 3, 6, and 12 months after the DWEK/DSO procedure or until subsequent treatment in the Study Eye for FECD. Subjects will also be seen as part of their regular health care, all relevant ocular assessments collected during this period will be recorded.

### **6.5.4** Early Termination Visit

If a subject is discontinued from study treatment early or withdraws from the study, he/she should be assessed approximately 28 days following the last study treatment administration; if the subject is unable to be evaluated approximately 28 days following the last study treatment administration, he/she should be evaluated as soon as practicable (at least by telephone). All assessments scheduled for Day 28 should be performed at the Early Termination Visit if Day 28 visit has not already been completed, otherwise assessments scheduled for Day 56 should be collected.

#### 6.5.5 Unscheduled Visit

Study subjects may be seen at any time in between scheduled study visits at the discretion of the Investigator and any relevant study assessments performed. The date and reason for the unscheduled visit will be recorded as well as the results of the relevant assessments.

### 6.5.6 End of Study Visit

An End of Study Visit (EOS) will be performed on all subjects. The EOS may be conducted any time after Day 168, during the EOS assessments scheduled for Day 336 will be performed and a plasma sample for ADA analysis will be collected. If the subject has already completed the study, the subjects should be contacted and asked to provide a plasma sample for ADA. Any subject who did not have gradeable specular images at their most recent visit should be reimaged and gradable images obtained.

Amendment 7.0: September 22, 2022

- Comprehensive Eye Examination
- Specular Image Collection
- Assessment of Corneal Thickness
- Assessment Best Corrected Visual Acuity
- Plasma sample collected for ADA

### **6.6 Pregnancy**

Subjects will be instructed to notify the Investigator as soon as possible after becoming pregnant or learning of the pregnancy of a partner. If a subject or partner of a subject becomes pregnant during treatment or up to 120 days following the last study drug administration, the Investigator is instructed to notify Trefoil (or designee) within 24 hours of learning of the pregnancy.

If the subject becomes pregnant while receiving investigational product, the investigational product will be permanently discontinued. Protocol-required procedures for study discontinuation and follow-up must be performed on the subject unless contraindicated by pregnancy. Other appropriate pregnancy follow-up procedures should be considered if indicated.

If the partner of a study participant becomes pregnant, the Investigator is instructed to obtain a Pregnant Partner Release Form and collect relevant information regarding the partner and the pregnancy. The Investigator will discuss the risks and concerns of investigational drug exposure to a developing fetus and counsel the subject and/or pregnant partner (or ensure that such counseling is provided).

Pregnancies will be followed through the outcome of the pregnancy. Newborns should be followed for a minimum of 8 weeks. The Investigator will complete a Pregnancy Surveillance Form and report the information regarding the pregnancy, outcome, and status of the newborn, as appropriate.

#### 7. ASSESSMENT OF EFFICACY

As described above, the efficacy endpoints will be visual acuity and endothelial cell count/density as measures by specular microscopy. Other efficacy assessments include:

- Slit lamp biomicroscopy assessments
- Central corneal thickness
- IOP

The primary efficacy timepoint is Day 28.

#### 8. ASSESSMENT OF SAFETY

#### **8.1 Adverse Events**

Investigators will collect information related to adverse events (AEs) throughout this clinical trial. The terms and definitions are consistent with *Guidance for Industry and Investigators Safety Reporting Requirements for INDs and BA/BE Studies, FDA 2012.* 

Amendment 7.0: September 22, 2022

- All AEs occurring in all subjects following exposure to study treatment until 28 days after each study treatment will be reported.
- AEs considered related to the study treatment by the Investigator (SARs) and SAEs will be followed until resolution, return to baseline, or stabilization (if resolution is not expected).

Changes in the subject's medical condition that occur prior to the first exposure to study treatment will be reported as medical history. At each post-treatment visit, subjects will be asked about any possible adverse events in a non-leading manner. An example of a non-leading method of eliciting AE information is "Have there been any changes in your health since you were here last?" Subjects should also be asked about the severity and/or persistence of any AEs that were ongoing at the time of their last visit.

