# **Study Treatment Group 2:**

Approximately 48 to 72 hours prior to DWEK/DSO (Day -3), study subjects will receive a "conditioning dose" (10ng [10mcL]) of TTHX1114. The conditioning dose is intended to provide anti-apoptotic protection for the existing cells. On Day 0, subjects will undergo DWEK/DSO and will receive TTHX1114 (50ng [50mcL]) at the time of the surgical procedure. As described above, the immediate post-surgical anterior chamber should easily accommodate the additional volume.

Study subjects will then return for follow-up on Day 1 (the day after DWEK/DSO) and subsequent study treatment administration on:

- Day 7
- Day 14
- Day 21

Follow-up visits will occur on:

Clinical Study Protocol TTHX-002

Confidential and Proprietary

Amendment 7.0: September 22, 2022

- Day 28
- Day 56

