# **Study Treatment Group 3:**

On Day 0, subjects will undergo DWEK/ DSO and will receive TTHX1114 (100ng [100mcL]) at the time of the surgical procedure. As described above, the immediate post-surgical anterior chamber should easily accommodate the additional volume.

Study subjects will then return for follow-up on Day 1 (the day after DSO) and subsequent follow-up visits will occur on:

- Day 7
- Day 14
- Day 21
- Day 28
- Day 56

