# 6.1.1 Descemetorhexis without Endothelial Keratoplasty (DWEK)/ Descemet Stripping Only (DSO)

Patients with FECD who have a planned DWEK/DSO or DMEK procedure will be evaluated for eligibility in this study. As the DWEK/DSO procedure is not a study procedure DWEK/DSO will be done according to institutional policy with a descemetorhexis area of 4 to 5mm. The method of surgery many include the use of the Sinskey Hook (with or without forceps) or an irrigation/aspiration (I&A) tip. The method of surgery will be at the discretion of the Investigator and Investigators will be selected based on their demonstrated expertise (e.g., historical number of procedures and relative success rate). The Lead Investigator may assist in the selection of investigational sites and the vetting of Investigators. Only qualified and vetted ophthalmologists will perform the surgical procedure on subjects enrolled in this study to minimize operator variability. Subjects with a descemetorhexis area of > 5mmwillbe excluded from efficacy analyses but will be included in the safety analyses.

AS-OCT should be performed at least 1 time following DSO (e.g., Day 28) to confirm the size of the descemetorhexis area, especially in subjects with delayed recovery.

Amendment 7.0: September 22, 2022

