#### **8.2.3** Adverse Event Duration

The start date (the date that the event was first noticed) and the end date (the date that the event had completely resolved or returned to baseline) will be recorded. If the exact date is not known, the best estimate should be reported.

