**Table 12: Analysis Sets** 

Analysis Set	Description of Population	Reference
Full Analysis Set*	
 
Received any study treatment (at least 1 complete or partial dose)
 
	ICH E9 (5.2.1)
Per Protocol Set	Met all eligibility criteria	ICH E9 (5.2.2)
	Have received all study treatments per protocol	
	
 
Underwent DWEK/DSO of 4 to 5mm
 
	
	
 
Have sufficient data collected for the accurate assessment of study endpoints
 
	

\*The Full Analysis Set will be used for the Safety Population

The Per Protocol Population will be used to assess the primary and secondary efficacy endpoints compared to the control group.

The Safety Population set includes all participants in participants who received any TTHX1114 and will be the population for safety outcomes; this population will be compared with the control group. Ocular AEs involving the study eye will be tabulated. Ocular AEs for the fellow eye and non-ocular AEs will be provided as a listing.

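### Section 8.1 starts adverse event reporting at the first TTHX1114 dose, so an intraoperative event before the Day 0 injection can be medical history in Groups 3 and 4 but an AE in Group 2

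*Combined protocol and SAP*

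**What the plan says.** Two sentences in Section 8.1 set the start of AE reporting. The first bullet reads "All AEs occurring in all subjects following exposure to study treatment until 28 days after each study treatment will be reported". The later sentence reads "Changes in the subject's medical condition that occur prior to the first exposure to study treatment will be reported as medical history".

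Two other places indicate what study treatment means. Table 12 defines the Full Analysis Set, which is also the Safety Population, by "Received any study treatment (at least 1 complete or partial dose". Section 6.1.1 says of the operation: "As the DWEK/DSO procedure is not a study procedure DWEK/DSO will be done according to institutional policy". The schedules of events also label the intracameral injection as the study treatment.

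First dose and operation fall in a different order by group:

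- Group 2: "Approximately 48 to 72 hours prior to DWEK/DSO (Day -3), study subjects will receive a" conditioning dose.
- Groups 3 and 4: the first dose is on Day 0 at surgery. For Group 3, Section 4 explains that "the immediate post-surgical anterior chamber should easily accommodate the additional volume", so the operation comes before the injection. Group 4 has the same Day 0 injection.
- Group 1: no TTHX1114 at all.

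Section 9.2 plans to summarise how many subjects, and what percentage, have any ocular AE in the study eye.

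**The concern.** The clock for AE reporting starts at the drug, while the setting in which safety is judged is the operation. Where the drug comes first, the whole operation lies inside the reporting window. Where the drug follows the operation, the intraoperative interval lies outside it. The same event, such as an intraoperative bleed, is then filed differently according to group.

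This matters because Section 3 makes safety in the DWEK/DSO setting part of the primary objective, and the planned safety summary is a simple percentage of subjects with an event. Groups 3 and 4 are planned at 20 subjects each, against 9 enrolled in Group 2. A start rule that leaves out part of the surgical period in the two largest groups can only lower their percentage.

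**Working it through.** The protocol gives no complication rate and no figure to reproduce. The check sets the passages side by side and then adds a calculation for scale.

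**Step 1. One event, four groups.** Take an intraoperative complication in a first treated eye that begins before the Day 0 injection, in a subject with no earlier TTHX1114.

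| Group | First dose | Has exposure begun when the event starts? | Status under Section 8.1 as written |
|---|---|---|---|
| 1 | none | never | no AE window opens |
| 2 | Day -3 | yes | AE |
| 3 | Day 0, after surgery | no | medical history |
| 4 | Day 0, after surgery | no | medical history |

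**Step 2. Cases outside the table.** A fellow eye re-enrolled in Group 3 or 4 under Section 6.1.2 may belong to a subject already dosed, and Section 5 admits subjects dosed in TTHX-001 to Group 3. For them the first exposure has arguably already happened. If the operation is more than 28 days after the last dose, an intraoperative event can fall under neither sentence of Section 8.1.

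**Step 3. Text that points the other way.**

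- Section 4.2 says that all AEs are recorded whatever their suspected cause, and gives no time window.
- Section 8.2.4 describes study treatment as drug or procedure when causality is assessed. It does not say whether the procedure is the operation or the injection.
- Tables 1, 3 and 4 mark AE assessment on Day 0. The note to Tables 3 and 4 puts assessments before the injection by default. Table 1 does so for a group that is never dosed.

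None of these says that a pre-injection surgical event is an AE, and Section 8.1 says specifically that it is medical history. The passages need to be reconciled.

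**Step 4. Ordering Day 0 events afterwards.** Section 8.2.3 asks for a start date and an end date and mentions no clock time. A Day 0 event therefore cannot be placed before or after a Day 0 injection from the AE dates alone.

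**Step 5. Scale, on an assumed rate.** Let p be the share of subjects with a complication that begins before the injection. The values of p are assumptions. Table 7 gives n = 20 + 20 = 40 for Groups 3 and 4.

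Expected subjects = n × p. Chance of at least one = 1 − (1 − p)^n.

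| Assumed p | Expected, Groups 3 and 4 (n = 40) | Chance of at least one | Expected, Group 2 (n = 9), counted as AEs |
|---|---|---|---|
| 2% | 40 × 0.02 = 0.8 | 1 − 0.98^40 = 0.554 | 9 × 0.02 = 0.18 |
| 5% | 40 × 0.05 = 2.0 | 1 − 0.95^40 = 0.871 | 9 × 0.05 = 0.45 |
| 10% | 40 × 0.10 = 4.0 | 1 − 0.90^40 = 0.985 | 9 × 0.10 = 0.9 |

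As a share of 40 subjects, 0.8 to 4.0 is 2 to 10 percentage points. These are ceilings. The loss is smaller if enrolment stops short of 40, if the subject has another study-eye AE, if the subject was dosed earlier, or if sites report such events anyway.

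**The case against.** **The rule follows the definition of an AE.** Section 8.1.1.1 ties an AE to use of a drug. In Groups 3 and 4 a pre-injection event precedes any TTHX1114, whereas a Group 2 subject already has drug on board, so the two events look alike but differ in exposure. This stands. It is a reason to show counts from both starting points, and not to make the count from surgery the leading one. It does not remove the need for a starting point that sites apply in the same way.

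**A reader might infer that capture is complete in Group 2 and nil in Groups 3 and 4.** The documents do not support that. The passages in Step 3 give a site good reason to record the event, and actual practice is unknown.

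**A reader might infer that serious intraoperative events would be lost.** Section 8.3 requires every SAE to be reported, whatever its cause, and sets no start point. Losing them would mean importing the Section 8.1 rule into Section 8.3, which the text does not do.

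**A reader might infer a biased safety comparison of Group 2 with Groups 3 and 4.** Sections 9.2 and 9.3.1 plan comparisons with the control group only. The issue is consistency of the ocular AE percentage if it is shown by group, not error in a planned test.

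**Relevant text may not be visible.** The Day 0 procedure, the section on Injection Feedback Forms and the AESI definitions in Section 8.4 have no content in the public copy. Section 12.1 keeps hospital charts and progress notes as source. Timing may therefore be recoverable, and it cannot be said that no time is recorded anywhere.

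**Conclusion.** The concern holds as an inconsistent rule. As written, Section 8.1 makes an intraoperative event before the Day 0 injection medical history in Groups 3 and 4 and an AE in Group 2, for a first treated eye with no earlier TTHX1114. This rests on reading study treatment as a dose, which Table 12, Section 6.1.1 and the schedules support and Section 8.2.4 leaves less certain. Because other passages point the other way, the likely result is classification that varies by site and by group.

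The study-eye ocular AE percentage in Groups 3 and 4 may be too low. The documents do not allow the amount to be estimated; the 0.8 to 4.0 subjects are a ceiling under assumed rates. The affected interval runs only from the start of surgery to the injection on the same day. Within the reporting window, events that begin after the injection are AEs in every dosed group.

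**What to change.** 1. Change both the first bullet and the medical-history sentence of Section 8.1. Suggested wording: *For each treated eye and in every group, AE collection starts at the earlier of the start of the DWEK/DSO procedure or the first TTHX1114 administration. Changes before that point are medical history; later events, including intraoperative events on Day 0, are AEs.* This also opens a window for Group 1 and covers fellow eyes. Align Sections 4.2 and 8.2.4 and the schedules with it.
2. Add a flag to the AE form for whether a Day 0 event began before or after the injection.
3. Query Day 0 medical-history entries already recorded and reclassify where needed.
4. Tabulate study-eye ocular AEs both from the start of surgery and from the first dose, and state this in the statistical analysis plan that Section 9.3 promises before database lock.

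The cost is a short text change, one tick-box, one round of queries and a second version of one table. The downside is that AE percentages in Groups 3 and 4 may rise slightly and will include some events that precede the drug; the flag separates these. No dose or clinical rule is affected.
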